## 8. CRITERIA FOR EVALUATION AND ENDPOINT DEFINITION

### 8.1 Primary Endpoint

A primary endpoint of the study is safety. Safety of the three escalating dose of WOKVAC will be assessed by adverse events as per CTCAE v4.0.

### 8.2 Secondary Endpoints

Secondary endpoints of the study include the immunogenicity of WOKVAC Th polyepitope plasmid based vaccine, antibody response to the three WOKVAC targets, memory T cell response, modulation of (Treg), and MDSC in patients with breast cancer at three escalating doses.

These secondary endpoints will be used to determine whether an immune response is observed between the three doses and to determine a recommended phase 2 dose for further cancer prevention studies as detailed in Section 13.5. Determining a phase 2 dose will be performed by key study personnel and NCI/DCP staff. The recommendation will be based on dose level safety/tolerance, immunogenicity, memory T cell response, T cell response, Treg and MDSC data.

### 8.3 Off-Agent Criteria

Patients may discontinue vaccines for the following reasons: completed the protocol-prescribed intervention, pregnancy, adverse event or serious adverse event, inadequate agent supply, noncompliance, concomitant medications, or medical contraindication. Patients may continue to be followed, if possible, for safety reasons and in order to collect endpoint data according to the schedule of events. Patients, who have persistent grade 3 or 4 toxicity (of a two week or greater duration), at time of withdrawal from study treatment, will continue to be followed until toxicity resolves or returns to baseline for that patient.

### 8.4 Off-Study Criteria

Participants may go “off study” for the following reasons: the protocol intervention follow-up period is completed including long term follow-up, adverse event/serious adverse event, lost to follow-up, noncompliance, concomitant medication, medical contraindication, development of cancer of the breast or other site, withdrawal of consent, death, determination of ineligibility (including screen failure), or pregnancy.

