### **5.7 Adherence/Compliance**

- 5.7.1. All patients who receive any vaccinations will be evaluated for primary endpoint of safety.
- 5.7.2. Patients who have baseline and at least one post vaccine research blood sample will be evaluated for immune response.
- 5.7.3. Compliance will be assessed by tracking visit dates and completion of protocol procedures.

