### **7.6 Long-Term Follow-up (LTFU) Period**

- 7.6.1. Information on patient's health status will be requested from the patient's primary oncologist or primary care physician annually from enrollment to complete 5 years. The following will be requested and reviewed:
  - a. Clinical notes
  - b. Laboratory values
  - c. Imaging reports

Notes will be reviewed by study team for vaccine toxicity such as site reaction and possible autoimmune symptoms (examples - unexplained rash, dry eyes, unexplained diarrhea) and overall relevant health status within the above collected records.

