#### 8.5.1. Criteria for Premature Study Termination

Benchmarks for the safety of a dose level will be that there are no attributable (definitely, probably and possibly-related to study drug) grade 4 toxicity and <30% incidence of attributable Grade 3 toxicity (definitely, probably and possibly related to the study agent except as noted in the table below). If the observed rate of each of these toxicities is consistent with these benchmarks, escalation to the next higher dose level will be allowed.

Escalation will not be allowed if the observed toxicity rate exceeds the above. Other participants at the same dose level without toxicities will be allowed to continue at that dose level.

For grade 1 or 2 vaccine-related reactions, patients may be treated with acetaminophen or diphenhydramine as clinically indicated at the discretion of the study clinician and continue to receive vaccinations. For this prevention study  $\geq$  grade 3 attributable toxicity (other than those listed below; CTEP CTCAE v4.0) is considered dose-limiting for the patient. If grade 3 toxicity that is at least possibly related to the vaccine (except as described below) is observed, no further immunizations will be administered to that patient.

If  $\geq 3$  participants experience a grade 3 attributable toxicity, except as noted in the table below, or if any participant experiences a grade 4 attributable toxicity within any dose level, further accrual at that dose level will stop and accrual to the study will be terminated.

Category	Grade 3 Attributable Toxicity/AE	Allowable Duration
General disorders and administration	Flu-like symptoms	1 week
Musculoskeletal and connective tissue disorders	Arthralgia	1 week
	Myalgia	1 week
Investigations	Lymphocyte count decreased	2 weeks
	Platelet count decreased	1 week
	Hemoglobin decrease	1 week
	White blood cells decreased	2 weeks

We would consider a grade 3 or 4 autoimmune event a dose limiting toxicity and would consider steroid administration for grade 3 or 4 adverse immune related events that have been reported with other immune based therapies, i.e. ipilimumab. Examples of such immune related AEs include; rash, diarrhea/colitis, and hepatitis. The following dose schedule may be used:

Day 1-2: Intravenous Solu-Medrol at 1 mg/kg  
Day 3-4: Prednisone at 30 mg BID PO q day  
Day 4-5: Prednisone at 15 mg BID PO q day  
Day 5-6: Prednisone at 10 mg BID PO q day  
Day 6-7: Prednisone at 10 mg PO q day  
Day 8-9: Prednisone at 5 mg PO q day

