
#### 8.5.1.1 Blood Glucose Monitoring

If random blood glucose is  $\geq 140$  mg/dl

1. Vaccine will be held and fasting glucose should be performed within a week:
  - a. If fasting glucose is  $\geq 100$  mg/dl patient should have a repeat fasting glucose done within 1 week
  - b. If fasting glucose is  $< 100$  mg/dl patient can receive vaccine
  - c. If this repeat fasting glucose remains  $\geq 100$  mg/dl patient will not receive additional vaccinations.

Patients who do not receive any more vaccines should continue to be followed for adverse events and immunogenicity.

For hyperglycemia with symptomology, please contact the IND Sponsor and DCP Medical Monitor.

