### **11.3 Long-Term Follow-Up (LTFU)**

Long-term follow-up will continue through review of clinical notes, lab values, and imaging reports requested annually from the participant’s primary oncologist or primary care provider.

Each site will be responsible for requesting the selected medical records from their participants’ primary oncologist or primary care provider. The collected information will be abstracted to record any possible autoimmune reactions and relevant health status.

This information will be reported annually to the FDA in order to satisfy their LTFU reporting requirements.

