### 13.6 Outcome measures

1. Primary endpoints: Safety through 6 month follow-up visit will be assessed per CTEP CTCAE v. 4.0.
2. Secondary endpoints:
  - a. Immunogenicity will be evaluated via an assessment of the generation of IGFBP-2, HER2, and IGF-1R specific IFN-g and IL-10, IFN-g/IL-10 ratios, inducing T cells, Th1:Th2 ratios and IgG antibodies.
    - (i) Cellular immune response will be defined by the magnitude of the Th1 (IFN-gamma (g)) antigen specific immune response using ELISPOT. Successful immunization will be defined by generating a protein specific IFN-g precursor frequency greater than 1:20,000 PBMC for each antigen. In patients with pre-existent immunity, responses must augment over 2 times baseline for immunization to be considered successful.
    - (ii) Humoral immune response will be measured by ELISA and serum antibody avidity for IGFBP-2, HER2, and IGF-1R to determine an avidity index (AI) before and after vaccination. Low avidity antibodies will have an AI <30%, moderate avidity antibodies 30-50% and high-avidity

antibodies 51-100%. Patients will be considered to have developed an IGFBP-2 antibody response if antigen specific IgG antibodies are both detectable and have moderate avidity.

- b. To detect persistent T cell memory, flow cytometry panels will be used to evaluate antigen specific central and effective memory phenotypes prior to and at 1 and 6, months after immunizations have ended for all 3 doses.
- c. To detect modulation of Tregs and MDSC with vaccination, levels over the course of immunization will be assessed by flow cytometry of PBMC.
- d. Long-term safety including vaccine toxicity and overall relevant health status.

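### Section 8.4 lets vaccinated patients leave the study for health-related reasons before year 5, and nothing shown provides for finding new safety events after they leave

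*Combined protocol and SAP*

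**What the plan says.** Section 8.4 gives completion of follow-up, long-term follow-up included, as one reason for going off study. It lists others beside it: "adverse event/serious adverse event, lost to follow-up, noncompliance, concomitant medication, medical contraindication, development of cancer of the breast or other site", then withdrawal of consent, death, ineligibility and pregnancy. Because these are separate from completion, they can apply before year 5. The wording is permissive, and the section has no clause on what happens after exit.

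Section 8.3 deals with stopping vaccine. It shares five of the six reasons at issue here (all but new cancer), and its general rule is optional: "Patients may continue to be followed, if possible, for safety reasons and in order to collect endpoint data according to the schedule of events". Section 8.5.1.1 is firmer, but only for patients stopped because of glucose: "Patients who do not receive any more vaccines should continue to be followed for adverse events and immunogenicity".

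Elsewhere the intent is wide. Section 5.7.1 states: "All patients who receive any vaccinations will be evaluated for primary endpoint of safety". Section 11.1.1 collects adverse events to the 6-month visit. Section 7.6 plans annual record requests to 5 years, and its purpose is explicit: "Notes will be reviewed by study team for vaccine toxicity such as site reaction and possible autoimmune symptoms". Section 11.3 places the task locally ("Each site will be responsible for requesting the selected medical records") and has the results reported to the FDA each year. Section 13.6, item 2d, makes this a secondary outcome: "Long-term safety including vaccine toxicity and overall relevant health status".

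**The concern.** The off-study list mixes reasons that make follow-up impossible or impermissible (death, lost contact, withdrawn consent) with reasons that are health events, their treatment, or poor compliance. In the second group the patient can usually still be followed, and some of these patients are among those a safety review most needs to keep. If they leave and nobody looks for later events, those still under review in years 2 to 5 could be a selected, healthier group. This is a first-in-human vaccine, and the long-term review looks specifically for autoimmune symptoms. A clean 5-year report could then mean either that nothing happened or that the patients to whom it happened were no longer observed.

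Two places make the gap more visible. Section 5.5 bars systemic steroids during the study and section 8.4 lists concomitant medication as an exit reason, yet in section 8.5.1 the investigators "would consider steroid administration for grade 3 or 4 adverse immune related events". The text does not say that patients so treated stay in follow-up. Pregnancy is also an exit reason, although section 4.1.8 calls fetal effects unknown and section 11.2.1 counts a birth defect as a serious adverse event. No section shown says that the pregnancy outcome is captured after exit.

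**Working it through.** **What continues after a patient stops vaccine or leaves**

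| Provision | Applies to | Finds new events after an off-study exit? |
|---|---|---|
| 8.3, general rule | Off-agent patients, optional | No; about stopping vaccine |
| 8.3, persistent grade 3 or 4 toxicity | Toxicity present at withdrawal from treatment | No; open event only |
| 8.5.1.1 | Glucose stops | No; about stopping vaccine |
| 11, laboratory events | Clinically significant event ongoing at last visit, up to 6 months | No; open event only |
| 11.1.5 | Clinically significant grade 3 or 4 events | No; open event only |
| 11.2.3 | Serious events | No; open event only |
| 13.3, telephone | Missed 1-month visit, optional | Not stated for off-study patients |
| 13.7 | Data of patients who drop out are kept | No; nothing on further collection |
| 7.6, 11.3, 12.1 | Annual records to year 5 | Silent on patients who left early |

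The event that prompts an exit is therefore recorded and, if serious or clinically significant at grade 3 or 4, followed. What is missing is ascertainment of later, new events.

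**Follow-up forfeited per exit.** The plan states no figure on this point. The 15% in section 13.3 covers only failure to receive all three vaccinations and the 1-month follow-up. Inputs: vaccines every 28 (+7) days, 6-month visit 168 ± 14 days after the last (7.1), 5 years counted from enrollment (7.6). Assumptions: no further delay to vaccination, and enrollment 0 to 21 days before vaccine 1.

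- Last vaccine: 2 × 28 = day 56 to 2 × 35 = day 70 after the first.
- 6-month visit: 56 + 154 = day 210 to 70 + 182 = day 252 after the first.
- From enrollment: 210 to 252 + 21 = 273 days, or 0.57 to 0.75 years.
- Remaining: 5 − 0.75 = 4.25 to 5 − 0.57 = 4.43 years.
- Share of 30 × 5 = 150 patient-years: 2.8 to 3.0%. Share of 36 × 5 = 180, if all 12 places per arm are used: 2.4 to 2.5%.

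**Effect on the long-term result.** The number of exits k is assumed, with 30 patients and no late event seen in those who remain.

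| k | Observed | Largest true proportion, k/30 | One-sided 95% upper bound had those k events been seen (Clopper-Pearson) | Zero-event upper bound if loss is unrelated to events, 1 − 0.05^(1/(30 − k)) |
|---|---|---|---|---|
| 0 | 0% | 0% | 9.5% | 9.5% |
| 1 | 0% | 3.3% | 14.9% | 9.8% |
| 3 | 0% | 10.0% | 23.9% | 10.5% |
| 6 | 0% | 20.0% | 35.7% | 11.7% |

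The third and fourth columns are a worst case in which every patient who left had an unseen late event; the true proportion could be anywhere from 0% to k/30. The last column shows the loss of precision alone, which is small. The concern is bias, and these precision figures do not measure it. The table also treats an exit as losing all late observation, whereas a patient who leaves in, say, year 3 still contributes the earlier annual reviews.

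**The case against.** A reader might infer that safety follow-up simply ends when a patient goes off study. The documents do not support that: sections 8.3, 11, 11.1.5 and 11.2.3 follow open events with no exemption for off-study patients, and section 13.7 keeps data already collected. A reader might also infer that patients will be lost. Section 8.4 only permits exit, and the commitments to evaluate everyone vaccinated (5.7.1, 13.8) and to request records to year 5 (7.6, 11.3) exclude nobody.

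Nor is it stated that steroid-treated or pregnant patients leave. Section 8.5.1 supplies the steroid schedule itself, and section 4.1.8 says only that a pregnant woman receives no more study treatment. These are ambiguities in the wording, not stated exits.

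It can further be said that after month 6 most listed reasons have little to act on, since vaccination is over and follow-up is chart review. New cancer is the main health reason left, and stopping there is defensible because new systemic therapy confounds attribution. Finally, the Data Management Plan, the Data and Safety Monitoring Plan with its addendum, and the University of Washington policy on long-term data are not shown and may say more.

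Most of this stands, and it narrows the point. It does not supply a rule for new events after exit. General intent does not settle the matter when section 8.4 names early exit as a separate status and the long-term sections do not mention patients in that status. Recurrence is foreseeable in patients with node-positive disease, and confounded attribution can be handled by separate tabulation without ending observation.

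**Conclusion.** The point holds in a limited form. Section 8.4 permits exit before year 5 for adverse events, noncompliance, concomitant medication, medical contraindication, new or recurrent cancer, and pregnancy, and no section shown provides for ascertaining new safety events afterwards. Mainly the 5-year safety outcome, and less so the endpoint to month 6, is open to selective loss.

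This is a risk, and its size cannot be derived from the documents. The exit counts of 1, 3 and 6 are assumptions, and the worst-case proportions are limits, not estimates. It would be wrong to infer that dose escalation or stopping is compromised: section 8.5.1 counts the grade 3 or 4 event itself, and an event that leads to exit has been recorded. Severity is minor to moderate. The conclusion depends on the unshown plans not already containing the missing rule.

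**What to change.** For vaccinated patients, move these six reasons out of section 8.4 so that they end vaccination only (8.3). Extend the principle of 8.5.1.1 to all of them as a requirement: adverse event collection through the 6-month visit, by telephone if a visit is not possible, and annual record requests to year 5. The exceptions are withdrawal of consent, death and loss to follow-up. State that steroids given under section 8.5.1 do not end follow-up. Keeping pregnant patients in record review also gives a route to the pregnancy outcome. Tabulate events after recurrence or new systemic therapy separately.

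The cost is protocol wording plus a few more calls and record requests; no extra vaccination or blood draw is needed for this safety follow-up. The downside is that events after recurrence or new therapy are harder to attribute, which is why they need their own table.

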### 8.5 Study Termination

NCI/DCP as the funding sponsor has the right to discontinue the study at any time.

#### 8.5.1. Criteria for Premature Study Termination

Benchmarks for the safety of a dose level will be that there are no attributable (definitely, probably and possibly-related to study drug) grade 4 toxicity and <30% incidence of attributable Grade 3 toxicity (definitely, probably and possibly related to the study agent except as noted in the table below). If the observed rate of each of these toxicities is consistent with these benchmarks, escalation to the next higher dose level will be allowed.

Escalation will not be allowed if the observed toxicity rate exceeds the above. Other participants at the same dose level without toxicities will be allowed to continue at that dose level.

For grade 1 or 2 vaccine-related reactions, patients may be treated with acetaminophen or diphenhydramine as clinically indicated at the discretion of the study clinician and continue to receive vaccinations. For this prevention study  $\geq$  grade 3 attributable toxicity (other than those listed below; CTEP CTCAE v4.0) is considered dose-limiting for the patient. If grade 3 toxicity that is at least possibly related to the vaccine (except as described below) is observed, no further immunizations will be administered to that patient.

If  $\geq 3$  participants experience a grade 3 attributable toxicity, except as noted in the table below, or if any participant experiences a grade 4 attributable toxicity within any dose level, further accrual at that dose level will stop and accrual to the study will be terminated.

Category	Grade 3 Attributable Toxicity/AE	Allowable Duration
General disorders and administration	Flu-like symptoms	1 week
Musculoskeletal and connective tissue disorders	Arthralgia	1 week
	Myalgia	1 week
Investigations	Lymphocyte count decreased	2 weeks
	Platelet count decreased	1 week
	Hemoglobin decrease	1 week
	White blood cells decreased	2 weeks

We would consider a grade 3 or 4 autoimmune event a dose limiting toxicity and would consider steroid administration for grade 3 or 4 adverse immune related events that have been reported with other immune based therapies, i.e. ipilimumab. Examples of such immune related AEs include; rash, diarrhea/colitis, and hepatitis. The following dose schedule may be used:

Day 1-2: Intravenous Solu-Medrol at 1 mg/kg  
Day 3-4: Prednisone at 30 mg BID PO q day  
Day 4-5: Prednisone at 15 mg BID PO q day  
Day 5-6: Prednisone at 10 mg BID PO q day  
Day 6-7: Prednisone at 10 mg PO q day  
Day 8-9: Prednisone at 5 mg PO q day

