### **13.3 Accrual and Feasibility**

The study will accrue 30 evaluable patients with up to 12 patients in each dose arm. We anticipate up to 15% of enrolled patients may fail to receive all three vaccinations and the 1 month post vaccine follow-up.

For information regarding the study population (including gender and minority considerations) please see Section 4.3 Inclusion of Women and Minorities.

In order to meet the primary objective of this study, AE information is collected at each of the study visits and reviewed by the study team on a regular basis. If patients are unable to complete to the one month post vaccination follow-up visit, AE information may be collected by phone if possible. For secondary objectives, the research samples will be batched after each cohort to achieve consistency in the assays.

When we batch the research samples we will run the baseline time point and post vaccine time point(s) for a patient (usually 4-5 patients at one time). With this we are looking at results of an individual (comparing their IFN-g response to their baseline) therefore the results can be analyzed together.

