### **13.7 Reporting and Exclusions**

If a patient drops from the study prior to becoming evaluable for immune responses, data will still be used to assess the safety of WOKVAC. In the event that an enrolled patient drops from the study for a reason other than a dose limiting toxicity (as defined in Section 8.5.1) prior to completing the 1-month post-vaccination follow up visit, then an additional patient will be enrolled onto the study, up to a maximum of 12 patients per dose level.

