### **13.9 Evaluation of Response**

The number of patients traditionally required to gather preliminary data on the safety of a dose in a phase I study is less than the number needed to evaluate immunologic responses and differences in the immunologic responses between cohorts of patients. Since Phase I tumor vaccine studies to date have proven to be relatively free of serious toxicity, the defining endpoint that would move a study forward to a more extensive phase II efficacy trial will likely be immunogenicity. In order to have meaningful immunologic data, the study will accrue 30 evaluable patients (10 patients per dose arm). When accrual is complete, we will: (1) determine if the WOKVAC vaccine elicits specific cellular and humoral immune responses for each antigen, and persistent antigen specific memory T cells can be detected and (2) which dose is most immunogenic. We expect that there may be differences in immune response between dose-levels. Moreover, the dose-level that is determined to be the most biologically relevant in terms of stimulating immunity may not be the highest dose.

Immune responses will be evaluated for patients who complete the vaccination series with both a baseline and a one month post vaccination series blood draw. Durability of generated immune responses will be evaluated in patients who complete the vaccination series with both a baseline and a 6 month post vaccination series blood draw.

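### Section 8.5.1 both allows escalation and ends study accrual when 3 of 11 or 3 of 12 vaccinated patients have attributable grade 3 toxicity

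*Combined protocol and SAP*

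**What the plan says.** Section 8.5.1 sets two dose-level rules for attributable grade 3 toxicity, both subject to the same table of exceptions.

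- **Escalation benchmark.** A dose level is acceptable with "no attributable (definitely, probably and possibly-related to study drug) grade 4 toxicity and <30% incidence of attributable Grade 3 toxicity". The section continues: "If the observed rate of each of these toxicities is consistent with these benchmarks, escalation to the next higher dose level will be allowed".
- **Termination trigger.** If three or more "participants experience a grade 3 attributable toxicity, except as noted in the table below", or if anyone has an attributable grade 4 toxicity, then "further accrual at that dose level will stop and accrual to the study will be terminated".

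Sections 3, 13.1 and 13.10 send the escalation decision back to 8.5.1 and add no denominator or precedence.

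On cohort size, Section 13.9 plans 10 evaluable patients per arm. Section 13.3 says "We anticipate up to 15% of enrolled patients may fail to receive all three vaccinations and the 1 month post vaccine follow-up". Section 13.7 replaces patients who leave before the 1-month visit for reasons other than dose-limiting toxicity, up to 12 per dose level.

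On who counts for safety, Sections 5.7.1 and 13.8 include everyone who was vaccinated, and Section 13.7 says of patients who drop out that "data will still be used to assess the safety of WOKVAC".

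**The concern.** One rule is a proportion and the other a count, so whether they agree depends on the cohort size. Both count the same events, yet opening the next arm and terminating accrual to the study cannot both happen.

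This is the escalation gate of a vaccine that, by Section 6.2, has not been given to humans before. If the rules diverge, key study personnel and NCI/DCP staff, who review each dose group under Section 13.10, would have to choose the denominator and the prevailing rule with the toxicity data already in front of them. Arm 3 has no higher dose, so the question concerns Arms 1 and 2 only.

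**Working it through.** **The plan's own cohort figure.** Ten evaluable patients with 15% loss need 10 / (1 − 0.15) = 11.8, rounded up to 12. This matches the stated cap of 12 per arm, so cohorts of 11 and 12 belong to the design.

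**The two rules at each cohort size.** Incidence is cases divided by patients vaccinated. All counts at n = 3 to 12 were compared with both thresholds; the informative rows are:

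| n | 2 cases | 3 cases | 4 cases |
|---|---|---|---|
| 7 | 28.6% | 42.9% | 57.1% |
| 10 | 20.0% | 30.0% | 40.0% |
| 11 | 18.2% | **27.3%** | 36.4% |
| 12 | 16.7% | **25.0%** | 33.3% |

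At n = 7 to 10 the rules agree: two cases pass both, and three fail both (3/10 is 30.0%, which is not below 30%). At n = 3 to 6 the benchmark can block escalation before the trigger is reached (2/6 = 33.3%), which is not a contradiction. Escalation is allowed and accrual terminated on the same data only at 3/11 and 3/12. With a fixed denominator of 10, three cases are always 30.0% and the conflict disappears.

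**How often an arm reaches 11 or 12.** Let d be the probability of a replaceable drop-out and N the cohort size reached by replacement until 10 are evaluable or the cap is hit. Then P(N=10) = (1−d)^10, P(N=11) = 10·d·(1−d)^10, and P(N=12) is the remainder.

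| d | N=10 | N=11 | N=12 |
|---|---|---|---|
| 5% | 59.9% | 29.9% | 10.2% |
| 10% | 34.9% | 34.9% | 30.3% |
| 15% | 19.7% | 29.5% | 50.8% |

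**How often the conflict arises.** The documents give no per-patient grade 3 rate, so the true rate p is assumed to lie between 5% and 30%. Let T3 be the position of the patient with the third case: P(T3=t) = C(t−1, 2)·p³·(1−p)^(t−3).

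- *Each outcome known before the next enrolment:* P(N≥11)·P(T3=11) + P(N=12)·P(T3=12). At p = d = 10%: 0.651 × 0.0194 + 0.303 × 0.0213 = 0.019.
- *Upper bound, ignoring early stopping:* P(N=11)·P(3 of 11) + P(N=12)·P(3 of 12). At p = d = 10%: 0.349 × 0.0710 + 0.303 × 0.0852 = 0.051.

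Each cell below gives the first figure, then the upper bound, in percent of arms:

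| p | d = 5% | d = 10% | d = 15% |
|---|---|---|---|
| 5% | 0.2 / 0.6 | 0.4 / 1.0 | 0.5 / 1.3 |
| 10% | 1.0 / 3.0 | 1.9 / 5.1 | 2.6 / 6.4 |
| 15% | 2.1 / 6.3 | 4.0 / 10.5 | 5.5 / 13.2 |
| 20% | 3.0 / 9.0 | 5.7 / 14.9 | 7.8 / 18.5 |
| 25% | 3.5 / 10.4 | 6.5 / 16.8 | 8.9 / 20.7 |
| 30% | 3.4 / 10.1 | 6.4 / 16.2 | 8.7 / 19.8 |

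If two more patients are enrolled before the third case is known, the range is 0.4% to 15.4%.

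**Consistency with the plan's loss figure.** The lower right of that table overstates the risk. After a non-exempt attributable grade 3 event, "no further immunizations will be administered to that patient", so a patient stopped after vaccine 1 or 2 fails to receive all three and already belongs to the 15% in Section 13.3. Let s be the share of grade 3 cases arising after vaccine 1 or 2, and set d = max(0, 15% − s·p). The highest values over p = 5–30% are then:

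| s | Known before next enrolment | Upper bound |
|---|---|---|
| 1/3 | 4.9% | 13.4% |
| 2/3 | 2.1% | 6.3% |
| 1 | 1.0% | 3.0% |

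**The case against.** The strongest reply is that the two sentences can be read together. Escalation is permitted, whereas termination is mandatory and covers the whole study; once accrual has ended, the permission has nothing to act on. Section 13.10 refers to the criteria of 8.5.1 in the plural, which suggests that all must be satisfied. This is the sensible reading, but no section states it. It would also leave the grade 3 benchmark without effect at 10 to 12 patients, where two cases are at most 20.0%. The text needs editing on either reading.

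Second, 8.5.1 does not adopt the all-vaccinated denominator. Sections 5.7.1 and 13.8 define who is evaluated for safety and do not tie that population to the 30% benchmark; at the planned 10 per arm the rules coincide. That is correct, and it is why the denominator has to be written down.

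Third, several things must coincide: at least one replaceable drop-out who had already been vaccinated, exactly three non-exempt grade 3 cases, no attributable grade 4, and a third case that occurs in, or is recognised after, patient 11 or 12. This stands and keeps the probability low. It does not make the case impossible. Section 3 staggers only the first patients of an arm, and adverse events are collected through the 6-month visit, so an arm may be full before the third case is known.

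**Conclusion.** The concern holds. With all vaccinated patients as denominator, exactly 3 of 11 or 3 of 12 in Arm 1 or 2 meets the condition to escalate and the condition to terminate accrual, and the plan does not say which governs.

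The arithmetic of the conflict is certain; its frequency depends on assumptions. The plan expects little toxicity (Section 13.8), and in two predecessor trials 99% and 96% of adverse events were grade 1 or 2 (Section 2.2), although those figures are per event and not per patient. This points to the low end: 0.2–0.5% of arms at a true rate of 5%, upper bound 0.6–1.3%. Over rates of 5–30%, with toxicity stops inside the 15% loss, the maximum is 1.0–4.9% when each outcome is known before the next enrolment, depending on when the events occur. The calculations assume independent patients and replaceable drop-outs who had at least one vaccination.

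The low probability limits the weight of the point. It should still be corrected, because the contradiction lies in the safety rule that opens the next dose.

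**What to change.** Reconcile the benchmark and the trigger in Section 8.5.1 so that together they give one instruction at every cohort size up to 12. State the denominator for the incidence and which rule prevails if the two differ. Have Sections 3, 13.1 and 13.10 point to that single rule. Which threshold, form and denominator to use is for the sponsor to decide; no position is taken here. The cost is protocol wording only, with no extra patients or procedures.
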